10.1 Analysis	
10.2 Sample Size	
11. Trial Steering Committee	
12. Data Monitoring Committee	
13 Direct Access to Source Data and Documents	
14 Ethics & Regulatory Approvals	
15 Quality Assurance	
16 Data Handling	.47

17 Data Management	
18 Publication Policy	
19 Insurance & Indemnity	
20 Financial Aspects	
21 Signatures	
References	

3. Background & Rationale

Antiphospholipid syndrome (APS) is the association of antiphospholipid antibodies (aPL) with both arterial and venous thromboses and/or obstetric morbidity (obstetric APS) [1].

We know that aPL are present in 20% of recurrent (three or more) first trimester miscarriages. Other obstetric complications are conditions associated with aPL-induced ischemic placental dysfunction, which include pre-eclampsia (PET), eclampsia, premature birth and fetal growth restriction (FGR) and stillbirth. Pregnancies in women with aPL are therefore considered as 'high risk', especially if women have a history of previous thromboses and/or obstetric complications. Current treatment regimens to prevent obstetric morbidity include low dose aspirin and low molecular weight heparin have improved pregnancy outcome but reduction in pregnancy loss remains sub-optimal.

Hydroxychloroquine is traditionally an antimalarial drug. Since the 1950's hydroxychloroquine has been widely used in the treatment of patients with rheumatoid arthritis or systemic lupus erythematosus (SLE). Hydroxychloroquine treatment of pregnant patients with SLE was first described more than three decades ago and its safety during pregnancy has been extensively documented and systematically reviewed [5-7]. APS is closely related to SLE, as up to 50% of patients with SLE have aPL[8].

Ostensen et al published their guideline for the use on anti-rheumatics in pregnancy more than a decade ago[7]. Their systematic review of several hundred pregnancies exposed to HCQ did not find any adverse pregnancy outcomes and recommended HCQ as the antimalarial of choice in women planning pregnancy and to be compatible with pregnancy and breastfeeding. In a recent update on this systematic review, which is the basis for the current British Society of Rheumatology (BSR) guidelines on HCQ in pregnancy, Flint et al. identified an additional 23 studies providing further information on 810 pregnancy exposures to HCQ. No specific pattern of congenital malformations was observed in association with HCQ exposure and it was concluded that HCQ is safe and is recommended as the 'immunmodulator of choice in pregnant women'[9]. These guidelines are in line with the European League against Rheumatism (EULAR) recommendations on the use of antirheumatics in pregnancy published in march 2017 [10].

The scientific basis for the use on HCQ is outlined below:

What is known about HCQ's action in the presence of aPL: basic science

Chloroquine and HCQ are weakly basic 4-aminoquinoline compounds. HCQ is the synthetic form of chloroquine and differs only by a hydroxyl group attached to a side chain resulting in a preserved efficacy with a less toxic side-effect profile [11]. The exact pharmacodynamics and action of HCQ *in vivo* remain to be fully uncovered, but most likely multiple molecular pathways are involved. HCQ's detailed effects in systemic lupus erythematosus (SLE) have been described elsewhere [12].

In retrospective clinical studies, HCQ was associated with a reduction in the risk of thrombosis in lupus patients and is discussed below. The mechanism by which HCQ might have an antithrombotic effect has been studied in a limited way. *In vitro* studies have showed that HCQ inhibits platelet aggregation and the release of arachidonic acid from aPL induced stimulated platelets [13]. Furthermore, Rand et al. showed

that aPL can disrupt the physiological anticoagulant shield of annexin A5 (AnxA5), leading to exposure of pro-coagulant phosphatidylserine and subsequently triggering thrombosis. As a novel finding, the group could show that HCQ restores the disruption of natural anticoagulant AnxA5 in patients with aPL [14].

Tissue factor (TF) is the key initiator of *in vivo* coagulation and has been implicated in in the pathogenesis of APS [15]. The ability of aPL to induce TF expression was demonstrated *in vitro* studies using serum samples from patients with purified aPL, which were added to cells, showing up-regulation of TF on monocytes [16, 17] neutrophils [18] and endothelial cells [19]. A number of investigators have found that serum, plasma, purified total IgG, antiB2GPI from APS patients increases TF expression and pro-coagulant activity on monocytes [20-22]. Lopez- Pedrera et al showed that anti-cardiolipin (aCL) IgG stimulate TF expression on circulating monocytes, acting through intracellular pathways including NFKappaB and MAP kinases [17]. In mice with aPL-induced fetal loss, neutrophils in turn can express TF through aPL–induced complement activation [23].

We have recently assessed the effect of using HCQ in patients with aPL and APS on plasma biomarkers including soluble TF, which has been shown to be increased in patients with APS. We showed that the use of HCQ was effective to decrease soluble TF levels in patients with aPL and APS 12 weeks after the commencement of HCQ compared to baseline [24]. This may be a mechanism contributing HCQ's antithrombotic effect.

Results from experiments in a *murine* model by Edwards et al. show that HCQ has the ability to reverse aPL-induced thrombosis [25]. The group observed that aPL-injected mice treated with HCQ had a significantly reduced thrombus size and that thrombus duration was reduced compared to mice treated with placebo [25]. *In vitro* studies showed that aPL are directly pathogenic towards trophoblast cells, which is a mechanism cited as a possible cause of recurrent first trimester pregnancy loss(es). *In vitro* studies have shown that HCQ reversed the aPL-induced inhibition of the chemokine interleukin 6 (IL-6) [26]. IL-6 released by first trimester trophoblast cells had been shown to drive trophoblast migration (a vital process for implantation) in previous studies by the same group [26].

Some studies support the hypothesis that the complement system is activated and plays a role in the pathogenesis of thrombotic and obstetric APS [23, 27-30]. Our group and others have previously confirmed complement activation in patients with isolated aPL and APS (thrombotic and obstetric APS) compared to healthy controls [30, 31]. Our most recent *in vivo* results assessing the effect of HCQ on complement activation markers C3-des-Arg and Bb in HCQ naive, non-pregnant aPL and APS patients at baseline and 12 weeks after the commencement of HCQ did not show any significant change in these values (Schreiber et al. The effect of treatment with hydroxychloroquine on biomarkers of hemostasis, complement, inflammation and angiogenesis in patients with antiphospholipid antibodies and antiphospholipid syndrome. Accepted in Rheumatology, 2017).

In mice exposed to complement inhibitors and knockout mice which have complement deficiencies there is inhibition of foetal loss and growth restriction mediated by aPL [23, 32] and also less aPL induced thrombus [27, 28]. Bertolaccini et al showed a possible protective effect HCQ of in a model of aPL-induced foetal loss [33]. In their mouse model, the fetuses died in 50% of pregnant aPL-injected mice and the survivors were growth-restricted and with smaller placentas compared to control mice. The administration of HCQ to mice exposed to aPL prevented fetal death, increased placental and fetal weight and decreased placental superoxide production (a marker of oxidative stress)[33]. In addition, the group reported HCQ-induced complement inhibition in APS patient serum, specifically looking at the

common pathway complement activation product C5a-des-Arg after receiving 6.5 mg/kg HCQ for 6 months [33].

At an intracellular level, *in vitro* studies show that aPL can induce endosomal NADPH (NOX) in endothelial cells and monocytes [34, 35]. NOX is an enzyme complex involved in pro-inflammatory signaling pathways [36]. Muller-Calleja et al recently published first *in vitro* data suggesting that HCQ significantly reduces the induction of endosomal NOX, which leads to a reduction of downstream gene activation [36]. This 'protective' mechanism of HCQ in preventing monocyte activation was confirmed in mice injected with human aPL [36].

What is known about HCQ's use in patients with systemic lupus erythematosus and APS: clinical studies

HCQ was the first drug licensed for the treatment of SLE and is one of the four currently licensed medications in SLE. The efficacy of HCQ in patients with SLE has been well described.

A cohort study of 150 SLE patients showed that it improves damage free survival [37], whereas data of 518 SLE patients from the observational LUMINA cohort showed that its use is associated with a reduced accrual of new disease damage. Ruiz-Irastorza performed a prospective observational cohort of 232 patients, showing an improved survival in SLE patients taking HCQ [38].

The antithrombotic effects of HCQ in patients with SLE was reported in data from the LUMINA cohort. In univariate analysis, including 442 SLE patients with aPL of whom 46 were identified having 51 recorded thrombotic events (over 1446 visits followed over a mean of 88 months), a protective effect of HCQ use was demonstrated (odds ratio [OR], 0.536)[39]. This finding is in line with an observational prospective cohort study of 232 SLE patients, in which Cox regression analysis showed that HCQ use was associated with a reduced risk thrombosis (seven events occurred while patients were taking HCQ, 7 further events happened after the patient had stopped HCQ whereas 28 events were reported in patients who had never taken HCQ, so yielding a hazard ratio [HR] of 0.28) [38]. Likewise, the antithrombotic effect of HCQ could also be demonstrated in several other cohort, case-control and retrospective studies [12].

The role of HCQ in APS is currently being investigated in thrombotic and obstetric APS. In a prospective non-randomized study of 40 patients with primary thrombotic APS without underlying SLE, Schmidt-Tanguy et al. studied the effect of 400 mg HCQ in addition to oral anticoagulation with vitamin K antagonists (VKA), target INR 2-3. None of the patients receiving HCQ along with standard anticoagulation had recurrent thromboembolic events, whereas 30% in the control group experienced a recurrent event (p=0.0086)[40].

In retrospective studies of pregnant patients with aPL and or APS, we and others showed that HCQ is a candidate for preventing aPL-related adverse pregnancy outcomes [41, 42].

In a retrospective multicenter cohort consisting of 30 APS patients (and 35 pregnancies), Mekinian et al reported that HCQ was associated with fewer first trimester miscarriages (pregnancy losses decreased from 81% to 19%, p<0.05) and improved live birth rates in refractory obstetric APS to 78% (p<0.05)[41]. In our retrospective observational cohort study of 96 women with 170 pregnancies, we also showed that HCQ treatment was associated with a higher rate of live births (67% in HCQ treated vs. 57% in untreated patients, p=0.05) and a lower prevalence of pregnancy morbidity (47% vs. 63%, p=0.004). Pregnancy duration was longer in patients receiving HCQ compared to those who did not receive HCQ (median 27.6 weeks, range [6-40] versus 21.5 weeks [6-40], p=0.03) and foetal losses beyond the 10 weeks of gestation were less frequent in women who were treated with HCQ (2%

vs. 11%, p=0.05). Moreover, ischaemic placental mediated complications (preeclampsia, eclampsia and foetal growth restriction (FGR) were less prevalent in HCQ treated women than in the control group (2% vs 10.9%, p=0.05). There was a significantly higher rate of women undergoing spontaneous vaginal labour in HCQ women compared to women without HCQ treatment (37.3% vs. 14.3%, p=0.01). The association of HCQ with the absence of aPL-related complications in pregnancy was confirmed in multivariate analysis (OR 2.2; 95% CI 1.2-136.1; p=0.04)[42]. In none of the above mentioned studies any fetal abnormalities were observed [41, 42]. We also conducted a systematic review of the evidence of HCQ in obstetric APS, which confirmed a lack of evidence. We therefore performed an expert based clinical judgement consensus, an accepted approach to address a specific and clinically relevant question in an area were best clinical practice is uncertain. The experts agreed that HCQ could be of benefit in certain circumstances in pregnant women with aPL [43].

The only solution to assess the effect of HCQ on pregnancy outcomes in women with aPL is to conduct a randomized controlled trial (RCT) of HCQ versus placebo. This trial will be the first of its kind and will lead to evidence-based recommendation on the use of HCQ in women with aPL.

4 Trial Objectives and Design

4.1. Trial Objectives

1. To study the effect of hydroxychloroquine on pregnancy outcome in women antiphospholipid antibodies.

To collect blood samples for pharmacokinetic and biomarkers studies

4.1.1 Primary endpoints

The primary endpoint is a composite of three principal aPL-related adverse pregnancy outcomes: one or more miscarriage (either < 10 weeks gestation or between 10 and 27+6 weeks gestation) and premature birth before 34 weeks due to any of: pre-eclampsia, eclampsia, fetal growth restriction (FGR) or stillbirth (i.e. after 24 weeks).

Premature birth for other reasons will not be included.

The components of the primary endpoint will each be presented as secondary endpoints (below).

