Primary objective	To study the effect of HCQ on pregnancy outcome in women with antiphospholipid antibodies.
Secondary objective	To collect blood samples for pharmacokinetic and biomarkers studies
Trial Design	A randomized controlled trial of HCQ versus placebo supplementing usual medication during pregnancy in women with antiphospholipid antibodies (aPL).
Endpoints	The primary endpoint is a composite of three principal aPL-related adverse pregnancy outcomes: one or more pregnancy loss(es) (either < 10 weeks gestation or beyond 10 weeks of gestation of a morphologically normal fetus documented by ultrasound or by direct examination of the fetus) and premature birth of a morphologically normal neonate before 34 weeks due to any of: pre- eclampsia, eclampsia, recognized features of placental insufficiency

	Premature birth for other reasons will not be included.
	The components of the primary endpoint will each be presented as secondary endpoints (below).
	 The pre-defined secondary endpoints include: Pregnancy loss < 10 weeks gestation Pregnancy loss > 10th week of gestation of a morphologically normal fetus documented by ultrasound or by direct examination of the fetus Premature birth of a morphologically normal neonate < 34 weeks due to any of: pre-eclampsia, eclampsia, recognized features of placental insufficiency. Gestational age at delivery Birth weight Delivery by Caesarean section Apgar score < 7 at 5 min Neonatal morbidity (bleeding or thrombotic complications, infections, congenital abnormalities) Days to hospital discharge following delivery (mother & child) Thrombotic events in the mother during pregnancy and 6 weeks post-partum. Days of neonate in special care Safety and tolerability of hydroxychloroquine in the mother and in the neonate
Sample Size	328 pregnant women (in order to achieve this number we will randomize 400 patients)

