8.1.1 Primary Efficacy Parameters

The primary efficacy parameters will include the absence of pregnancy complications, i.e. as defined in the primary endpoint is defined as follows:

The primary endpoint is a composite of three principal aPL-related adverse pregnancy outcomes: one or more pregnancy loss(es) (either < 10 weeks gestation or beyond 10 weeks of gestation of a morphologically normal fetus documented by ultrasound or by direct examination of the fetus) and premature birth of a morphologically normal neonate before 34 weeks due to any of: pre-eclampsia, eclampsia, recognized features of placental insufficiency Premature birth for other reasons will not be included.

The components of the primary endpoint will each be presented as secondary endpoints (below).

The pre-defined secondary endpoints include:

- 1. Pregnancy loss < 10 weeks gestation
- Pregnancy loss > 10th weeks of gestation of a morphologically normal fetus documented by ultrasound or by direct examination of the fetus
- 3. Premature birth of a morphologically normal neonate < 34 weeks due to any of: pre-eclampsia, eclampsia, recognized features of placental insufficiency.
- 4. Gestational age at delivery
- 5. Birth weight
- 6. Delivery by Caesarean section
- 7. Apgar score < 7 at 5 min
- 8. Neonatal morbidity (bleeding or thrombotic complications, infections, congenital abnormalities)
- 9. Days to hospital discharge following delivery (mother & child)
- 10. Thrombotic events in the mother during pregnancy and 6 weeks post-partum.
- 11. Days of neonate in special care
- 12. Safety and tolerability of hydroxychloroquine in the mother and in the neonate

The components of the primary endpoint will each be presented as secondary endpoints.

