8.2 Procedures for Assessing Efficacy Parameters

The primary outcome of the HYPATIA study will be a composite of pregnancy complications as defined above (see primary and secondary outcomes).

Adverse pregnancy outcomes are defined under 'Glossary and Definition' (Section 2). Each adverse pregnancy outcome will be recorded for each individual case. Fetal growth will be assessed by using standardized ultrasound methods. Pre-eclampsia will be diagnosed according to international criteria (see definition in section 2), information with regards to the baby, i.e. gestational age at delivery, birth weight, mode of delivery, Apgar < 7 at 5 min, neonatal morbidity (bleeding or thrombotic complications, infections, congenital abnormalities), number of days in hospital and thrombotic events in the mother during the puerperium. Patients will be consented to give the trial team access to their child's hospital notes if needed (i.e. in case of admission to paediatric special care units or complications such as intraventricular haemorrhage).

Symptoms suggestive of VTE will be evaluated according to the usual diagnostic methods. Patients who present with symptoms suggestive of stroke, myocardial infarction or arterial thrombosis at other sites, generally present as a clinical emergency and clinical and diagnostic information will be obtained retrospectively from the center at which they have been managed.

Efficacy makers are defined as follows:

Miscarriage: The presence of a miscarriage will be determined due to standard medical practice at each participating unit. Usually this will include a history from the patient and at some centers ultrasound for confirmation.

Fetal death: This will be determined by ultrasound according to standard medical practice.

Intrauterine growth restriction: Serial ultrasound assessments according to standard medical practice and the use of growth percentiles will be used to determine the presence or absence of fetal growth restriction (individualized birth weight according to Gardosi).

Placental abruption: Patient history and ultrasound according to standard medical practice.

Premature birth: Birth between 24+0 and 36+6 weeks gestation.

Pre-eclampsia as defined in international guidelines [4]: Hypertension developing after 20 weeks gestation and the coexistence of one or more of the following new onset conditions:

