9.2.1 Adverse events that do not require reporting

Pregnancy itself is well known to potentially causing nausea and tiredness due to several physiological adjustments of the body especially in the first trimester. Any symptoms thought to be related to the physiological changes in pregnancy do not require reporting.

In patients with aPL we expect pregnancy complications. Therefore, aPL related pregnancy complications, such as miscarriage < 10 weeks gestation, miscarriage > weeks 10, premature birth < 34 weeks due to pre-eclampsia, eclampsia or FGR and stillbirth shall not be reported as SAE. For these events we have designed a special section in the electronic database 'adverse pregnancy outcomes', which shall be completed in this case. Any other adverse events will be reported.

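### The primary endpoint is defined in two incompatible ways, so the same pregnancy can be an event in one section of the protocol and not in another

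*Protocol*

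**What the plan says.** The protocol states the primary endpoint in three places.

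- **Section 4.1.1 (Primary endpoints).** The loss part is "one or more miscarriage (either < 10 weeks gestation or between 10 and 27+6 weeks gestation". The preterm part is "premature birth before 34 weeks due to any of: pre-eclampsia, eclampsia, fetal growth restriction (FGR) or stillbirth (i.e. after 24 weeks". Neither part has a morphology condition, and placental insufficiency is not named.
- **Section 8.1.1 (Primary Efficacy Parameters).** The loss part is "either < 10 weeks gestation or beyond 10 weeks of gestation of a morphologically normal fetus documented by ultrasound or by direct examination", with no upper gestational limit. The preterm part is "premature birth of a morphologically normal neonate before 34 weeks due to any of: pre-eclampsia, eclampsia, recognized features of placental insufficiency".
- **Synopsis, Endpoints.** It matches 8.1.1, including "premature birth of a morphologically normal neonate before 34 weeks due to any of".

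All three say that other premature births do not count and that the components will be presented as secondary endpoints. The list that follows 4.1.1, in section 4.1.2, uses the components of the synopsis and 8.1.1. Section 9.2.1, on events exempt from SAE reporting, uses terms closer to 4.1.1: "premature birth < 34 weeks due to pre-eclampsia, eclampsia or FGR and stillbirth shall not be reported as SAE".

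The glossary (section 2) makes placental insufficiency wider than FGR. It covers abnormal fetal surveillance tests, abnormal Doppler and oligohydramnios as well as low birth weight for gestational age.

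**The concern.** A composite endpoint is a classification rule: each pregnancy is either an event or not. Here two rules are in force under the same name. They differ on fetal and neonatal morphology, on the upper gestational limit for a loss, and on which causes of early delivery count. Neither contains the other, so there is no conservative version to fall back on.

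The primary risk ratio and risk difference therefore depend on which section the analyst follows. If the choice is made late, it can be made with knowledge of how the results look. A reader of the final report would also be unable to say which endpoint was prespecified.

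**Working it through.** **1. The plan's own figure.** Section 10.2 gives 63% versus 47%, alpha 0.05, power 80%, 5% crossover and a total of 328. I assume a two-sided test and 1:1 allocation. With unpooled variance, n per arm = (0.63×0.37 + 0.47×0.53) × (1.960 + 0.842)² / 0.16² = 0.4822 × 7.849 / 0.0256 = 147.8, so 148 per arm and 296 in total. Allowing for crossover, 296 / 0.95² = 327.98, which rounds to 328. The arithmetic reproduces. The two rates are for aPL-related pregnancy morbidity in a retrospective cohort, and section 10.2 ties them to neither definition.

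**2. The same pregnancy under each text.**

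| Pregnancy | Section 4.1.1 | Synopsis and 8.1.1 |
|---|---|---|
| Loss at 15 weeks, fetus morphologically abnormal | Event (miscarriage, 10 to 27+6) | Not an event |
| Birth at 32 weeks for pre-eclampsia, malformed neonate | Event | Not an event |
| Birth at 32 weeks for abnormal Doppler or oligohydramnios, no FGR, no pre-eclampsia | Not an event (cause not listed) | Event (placental insufficiency) |
| Stillbirth at 36 weeks, normal fetus | Depends on reading | Event (loss beyond 10 weeks) |

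The first three rows follow directly from the wording. In the fourth, the grammar of 4.1.1 makes stillbirth a cause of birth before 34 weeks, so a death at 36 weeks is excluded. Read as a separate component starting at 24 weeks, it would be included.

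**3. Direction.** Rows 1 and 2 add events under 4.1.1. Row 3 adds events under the synopsis and 8.1.1, as does row 4 on the grammatical reading. Moving between texts could raise or lower the event rate.

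**4. What this could do to power.** The documents do not give the share of discordant pregnancies. As an assumption only, hold the relative effect at 47/63 with 164 per arm and no crossover, and vary the control rate:

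| Control rate | Power |
|---|---|
| 68% | 89% |
| 63% (planned) | 83% |
| 60% | 79% |
| 58% | 76% |

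This shows sensitivity in both directions. It is not an estimate of loss.

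**The case against.** **The definitions agree on many pregnancies.** Both count every loss before 10 weeks, a loss at 10 to 27+6 weeks of a documented normal fetus, and birth of a normal neonate before 34 weeks for pre-eclampsia or eclampsia. Most FGR deliveries also qualify under placental insufficiency through birth weight below the 10th percentile. This stands and limits how often the conflict bites. It does not remove it.

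**Section 4.1.1 looks like the outlier.** It refers to components listed below it, and 4.1.2 lists those of the synopsis and 8.1.1. A statistical analysis plan may already have chosen, and section 6.4.1 says the trial statistician knows only A versus B. This suggests which text was intended and reduces the risk of a choice driven by results. But the protocol never says which text prevails, and an analysis plan that picks one would still contradict a section of the protocol. Coded arms also still show the size of a difference.

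**Stronger readings that the documents do not support.**

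- *Placental-insufficiency births go unrecorded because 9.2.1 omits them.* The list there gives examples of events exempt from SAE reporting and is not an eCRF specification. Section 9.2 sends outcome events to the appropriate CRF, section 8.2 says each adverse pregnancy outcome is recorded, and the visit schedule collects growth scans and uterine artery Doppler.
- *Losses without documented morphology are scored as successes.* Section 8.2 says of miscarriage "Usually this will include a history from the patient and at some centers ultrasound for confirmation", but its next entry has fetal death determined by ultrasound. Morphology can also be documented by an earlier scan or by direct examination. No rule says how an undocumented loss is scored.
- *Power falls to about 74%.* That figure removes 10% of all events in each arm (56.7% versus 42.3%). Documentation of a lost fetus affects only losses beyond 10 weeks. In the retrospective cohort in section 3 these were 2% with HCQ and 11% without. Removing 10% of all events takes 4.7 points from the HCQ arm, more than all its late losses.
- *Fetal deaths at 24+0 to 27+6 are misclassified in 4.1.1.* They fit both miscarriage and stillbirth there, but count either way. No woman's status changes.

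**Conclusion.** The contradiction is real and lies in the current text. Section 4.1.1 conflicts with the synopsis, 4.1.2 and 8.1.1. Three types of pregnancy are classified in opposite ways on the plain wording, and a fourth (stillbirth of a normal fetus at or after 34 weeks) depends on how stillbirth is read in 4.1.1. Because this is the primary endpoint, it should be corrected.

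The number of women affected cannot be derived from the protocol, and the net effect on the event rate could go either way. No power loss is claimed, and the sample size calculation is not at fault. The conclusion rests on wording alone and needs no assumption about event rates.

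**What to change.** - Replace the 4.1.1 text so that one definition stands word for word in the synopsis, 4.1.1 and 8.1.1. Section 4.1.2 already follows the synopsis and 8.1.1.
- Use contiguous gestational bounds: below 10+0, and 10+0 or later with no upper limit, with stillbirth explicitly included. The present wording in 8.1.1 does not clearly place a loss at exactly 10+0.
- Bring the wording of 9.2.1 into line, and check that the adverse pregnancy outcomes form captures each placental-insufficiency criterion in the glossary.
- State how a loss at 10 weeks or later without documented morphology is classified, and run the alternative classification as a sensitivity analysis.
- Date the choice before anyone sees comparative data.

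The cost is amendment wording and an eCRF check, with no extra patients, visits or procedures.
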